4.12.6 Other Toxicities

Other treatment related toxicity attributed to the therapy will be captured, recorded and the consequences of should all be graded according to the CTCAEv4.

4.13 RT Quality Assurance Review

[name] will perform an RT Quality Assurance Review within 3 weeks after complete data for cases enrolled has been received.

5. DRUG THERAPY

5.1 Concomitant Medications/Treatments:

Patients will be allowed to receive chemotherapy at the discretion of the treating Gynecologic Oncologist except on day of delivery of *Image Guided Hypofractionated Radiation Treatment* fraction.

6. STUDY PROCEDURES

6.1 Screening/Baseline Procedures

Assessments performed exclusively to determine eligibility for this study will be done only after obtaining informed consent. Assessments performed for clinical indications (not exclusively to determine study eligibility) may be used for baseline values even if the studies were done before informed consent was obtained.

The screening procedures include:

- 6.1.1 Informed Consent
- 6.1.2 Medical history: Complete medical and surgical history, history of infections
- 6.1.3 Demographics: *Age, gender, race, ethnicity*
- 6.1.4 Review subject eligibility criteria
- 6.1.5 Review previous and concomitant medications
- 6.1.6 Physical exam including vital signs, height and weight
- 6.1.7 Zubrod performance status
- 6.1.8 Baseline adverse events will be assessed. See section 6 for Adverse Event monitoring and reporting.

6.2 Procedures at the End of Boost Therapy

- Toxicity (include DLT) evaluations
- FACT-CX QOL (optional)

6.3 Follow-up Procedures

Patients will be followed for 5 years after completion of treatment or until death, whichever occurs first. Patients removed from treatment for unacceptable adverse events will be followed until resolution or stabilization of the adverse event. Patients will be seen at clinic at 1 month, 3 months, 6 months, 12 month, 18 month, 24 month, then annual for 3 more years post-therapy for evaluation of disease progression as well as radiation toxicities.

- For the purposes of this protocol completion of therapy will be considered the day on which the fourth and final fraction of Image Guided Hypofractionated Radiation Treatment is delivered
- Any visit between one month and four month after the completion of therapy will be considered the three months visit
- Any visit between five months and eight months after completion of therapy will be considered the sixth month follow up
- Any visit between ten months and fourteen months after the completion of therapy will be considered the one year follow up
- Follow ups beyond one year can be scheduled \pm 2 month for each time point.

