6.3.1 Procedure

- At each follow up patients will receive a complete physical exam and receive assessment for toxicity
- Patient should receive axial imaging at least once within fourteen months after completion of therapy
- FACT-CX QOL (optional) at 3, 12 and 24 Months post-treatment follow-up visits.

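### Section 6.3 labels the scheduled 1-month visit as the 3-month visit, so an early FACT-Cx form can count as month 3 in the QOL analysis

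*Combined protocol and SAP*

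**What the plan says.** Section 6.3 sets the schedule: "Patients will be seen at clinic at 1 month, 3 months, 6 months, 12 month, 18 month, 24 month, then annual for 3 more years". Time zero is the end of the boost: "completion of therapy will be considered the day on which the fourth and final fraction" is delivered.

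The same section then assigns visits to time points. For month 3: "Any visit between one month and four month after the completion of therapy will be considered the three months visit". For month 6: "Any visit between five months and eight months after completion of therapy will be considered the sixth month follow up". For month 12: "Any visit between ten months and fourteen months after the completion of therapy will be considered the one year follow up". Later visits have a tolerance of 2 months either way. Nothing is said about a 1-month window, or about which visit counts when two carry the same label.

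Section 6.3.1 ties the questionnaire to named visits: "FACT-CX QOL (optional) at 3, 12 and 24 Months post-treatment follow-up visits". The Time and Events Table (6.4) adds forms before the boost and at its end. Section 8.5.1 analyses change in QOL by GEE, using the data available at six predetermined time points.

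**The concern.** The schedule and the labelling rule in Section 6.3 do not fit together. Two scheduled visits, two months apart, receive one label. The conflict arises when the schedule is followed, not only when a patient strays from it.

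It matters because one planned analysis uses the labels. If staff hand out the questionnaire at the first clinic visit inside the month-3 window, the form describes a patient about one month after the last fraction, while the analysis treats it as month 3. If she completes another at the true 3-month visit, nothing says which one counts. Whoever resolves this after the scores are in does so without a rule set in advance.

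**Working it through.** There is no stated figure to reproduce. The check maps the schedule to the windows, then compares the month-3 window with the protocol's own acute/late boundary.

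**Step 1. Scheduled visits against year-1 windows (Section 6.3, months after completion).**

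| Scheduled visit | Window it falls in | FACT-Cx due? (6.3.1, 6.4) |
|---|---|---|
| 1 | 1-4, labelled month 3 | No |
| 3 | 1-4, labelled month 3 | Yes |
| 6 | 5-8, labelled month 6 | No |
| 12 | 10-14, labelled month 12 | Yes |

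Months 1 and 3 share a label. This takes the lower limit as inclusive, but a 1-month visit held a few days late is inside the window on any reading. One held a few days early has no label. Between the year-1 windows, 4-5 and 8-10 months are unassigned. No nominal visit date falls there.

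**Step 2. The month-3 window on the clock from boost start.** Inputs: a boost of 2-3 weeks, or 14-21 days (Section 1.1); an acute period of under 90 days from boost start (Section 2.2.1); 365.25/12 = 30.44 days per month.

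- Window start = 30.44 + boost length: day 44 (14-day boost) to day 51 (21-day boost).
- Window end = 4 × 30.44 + boost length: day 136 to day 143.
- Window length = 3 × 30.44 = 91.3 days.
- Share before day 90 = (90 − window start)/91.3: (90 − 44.4)/91.3 = 0.50 and (90 − 51.4)/91.3 = 0.42.
- Day 90 in months after completion = (90 − boost length)/30.44: 2.5 and 2.3.

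Between 42% and 50% of the month-3 window is therefore acute time by the protocol's definition. A visit on the nominal 3-month date falls on day 105-112, in the late period. These are shares of calendar time, not of forms.

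**Step 3. Effect on the QOL estimate.** For a simple mean, shift = f × d. Here f is the fraction of month-3 forms completed early, and d is the average difference between the early score and the score the same patient would give at 3 months. The documents give neither, so no size follows. With at most 21 patients, one early form carries at least 1/21 = 4.8% of the weight, and more if some patients decline the optional form.

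**Step 4. Which other analyses use the labels?**

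- Toxicity: Sections 2.2.1 and 8.2 define the periods in days from the start of the boost or of protocol treatment. Section 8.5.1 uses proportions of treated patients. Section 8.5.2 times late events to onset. Section 10.3 counts to 90 days from the start of therapy. None uses a visit label.
- Primary endpoint: Section 8.5.1 analyses time to local failure by Kaplan-Meier and a one-sample log-rank test. It does not use the labels either.

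**The case against.** The strongest reply is that no FACT-Cx form is due at month 1. Sections 6.2, 6.3.1 and 6.4 place forms before the boost, at its end, and at months 3, 12 and 24. A form is mislabelled only if someone completes it early. That is correct, and it is why the effect is a possibility without a size. It does not remove the problem, because the rule accepts such a form as a valid month-3 form.

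Three stronger readings are tempting and are not supported.

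- A reader might infer that month-3 toxicity mixes acute and recovered patients. No month-3 toxicity estimate is planned. Only a by-visit toxicity table would be affected, and none is specified.
- A reader might add 14-16 and 20-22 months to the year-1 gaps and conclude that 1 + 2 + 2 + 2 = 7 of the first 24 months belong to no visit. The later intervals come from a scheduling allowance ("Follow ups beyond one year can be scheduled" with a tolerance), not from a labelling rule. Any of these gaps catches only an off-schedule visit, and some space between visit tolerances is ordinary.
- A reader might infer that out-of-window forms would be dropped. Section 8.5.1 calls for all available data at the predetermined time points and does not mention exclusion. What is missing is a rule, in either direction.

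**Conclusion.** The point holds as a minor one about QOL and data handling. Section 6.3 gives the 1-month and 3-month visits the same label, has no month-1 window and no rule for duplicates, and so lets a form from about one month after treatment enter the GEE analysis as month 3.

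The measurable part is the window: 3 months wide, containing a second scheduled visit, with about 42-50% of it in the acute period if the boost takes 2-3 weeks. The direction of any bias, toward acute effects, assumes that scores at one month still reflect acute treatment effects that have eased by month 3. Its size cannot be calculated from the documents.

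QOL is optional and secondary, and the planned toxicity and primary local-control analyses are unaffected. A related loose end is that Sections 8.2 and 8.5.1 refer to six QOL time points while Sections 6.3.1 and 6.4 identify five. The documents do not say whether month 1 was meant as the sixth.

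**What to change.** In Section 6.3, define analysis windows without changing the visit schedule:

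- Give the 1-month visit its own window and start the month-3 window after it. For example, month 1: after the end-of-boost assessment, up to 2 months; month 3: over 2 and up to 4.5 months. A form in the month-1 window then does not count as month 3.
- Assign a form that falls outside every window to the nearest scheduled QOL time point.
- When two forms share a window, use the one nearest the target date.
- Record the actual assessment date of each form, and say in Section 8.5.1 that it is available to the QOL model.

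With the example windows, month 3 would start at 2 × 30.44 + 14 = day 75 to 2 × 30.44 + 21 = day 82 after boost start and last 2.5 × 30.44 = 76.1 days. The share before day 90 falls to 15.1/76.1 = 20% or 8.1/76.1 = 11%. Some overlap with the acute period remains, which is a reason to keep the actual dates.

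The same edit should reconcile the number of QOL time points between Sections 6 and 8. The cost is wording only: no added visits, patients or procedures. It should be settled before QOL scores are examined.

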6.3.1 Procedure

- At each follow up patients will receive a complete physical exam and receive assessment for toxicity
- Patient should receive axial imaging at least once within fourteen months after completion of therapy
- FACT-CX QOL (optional) at 3, 12 and 24 Months post-treatment follow-up visits.

6.4 Time and Events Table

Schema	Prior to Boost Therapy	End of Boost Therapy	Follow-up
Informed Consent	X		
History and PE	X		X
Performance Status	X		X
Toxicity (include DLT) Evaluations		X	X
Tumor assessment	X ²		X ¹
CT, MRI or PET/CT	X ^{2,3}		X ¹
FACT-CX QOL (optional)	X	X	X M3, then years 1 & 2

¹Patient should receive axial imaging at least once within fourteen months after completion of therapy but preferably at 3 months after completion.

²Measurable lesions are not mandatory for patients to be enrolled to this study.

³The same technique should be used for both prior and after radiation treatments for tumor assessment.

6.5 Removal of Subjects from Study

Patients can be taken off the study treatment and/or study at any time at their own request, or they may be withdrawn at the discretion of the investigator for safety, behavioral or administrative reasons. The reason(s) for discontinuation will be documented and may include:

- 6.5.1 Patient voluntarily withdraws from treatment.
- 6.5.2 Patient withdraws consent)
- 6.5.3 Patient is unable to comply with protocol requirements
- 6.5.4 Patient demonstrates disease progression (unless continued treatment with study drug is deemed appropriate at the discretion of the investigator).
- 6.5.5 Patient experiences toxicity that makes continuation in the protocol unsafe.
- 6.5.6 Treating physician judges continuation on the study would not be in the patient's best interest.
- 6.5.7 Patient becomes pregnant during active treatment (pregnancy to be reported along same timelines as a serious adverse event).
- 6.5.8 Lost to follow-up. *Example language: If a research subject cannot be located to document survival after a period of 2 years, the subject may be considered "lost to follow-up." All attempts to contact the subject during the two years must be documented and approved by the Data Monitoring Committee.*

7.0 MEASUREMENT OF EFFECT

7.1 Antitumor Effect

Response and progression will be evaluated in this study using the new international criteria proposed by the Response Evaluation Criteria in Solid Tumors (RECIST) Committee [*JNCI* 92(3):205-216, 2000]. Changes in only the largest diameter (unidimensional measurement) of the tumor lesions are used in the RECIST v1.1 criteria.

7.1.1 Definitions

Evaluable for toxicity: All patients will be evaluable for toxicity from the time of their first treatment with radiation.

Evaluable for objective response: Only those patients who have clinically evaluable or measurable disease (by imaging) present at baseline, have received at least one fraction of Image Guided Hypofractionated Radiation Treatment, and have had their disease re-evaluated will be considered evaluable for response. These patients will have their response classified according to the definitions stated below. (Note: Patients who exhibit objective disease progression prior to the end of Image Guided Hypofractionated Radiation Treatment will also be considered evaluable.)

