4. RADIATION THERAPY

4.1 Dose Specification

- a. Initial Pelvic (+/- Para-aortic) fractionated external beam Radiation with 45 Gy to combined PTV with a boost to 55Gy for PET positive/CT enlarged nodes;
- b. Image Guided Hypofractionated Radiation Treatment boost to Cervix High risk CTV/PTV 28GY/4 fx.

Patients will receive 4 fractions of 7 Gy each via stereotactic body radiation as boost therapy to a volume that encompasses the cervical tumor. A minimum of 40 hours should separate each treatment.

4.2 Details of Planning for external Beam Pelvic RT:

Daily external beam radiation (with concurrent weekly cisplatin) will be preferably given using intensity modulated radiation therapy (IMRT) to the primary tumor in the cervix and pelvic lymphatics. The para-aortic lymph nodes will also be treated only if there is 18F-FDG uptake on the staging PET/CT scan. The following targets will be outlined.

- Gross tumor volume-node (GTV node): This will be designated by the 18F-FDG avid lymph node as outlined on the PET/CT scan.
- Clinical target volume-nodal (CTV nodal): This volume will be contoured as recommended by Consensus Guidelines For Delineation of Clinical Target Volume for Intensity Modulated Pelvic Radiotherapy in the Definitive Treatment of Cervix Cancer [33]
- Clinical Target Volume Cervix and Parametria (CTV cervix): This volume will be contoured as recommended by Consensus Guidelines For Delineation of Clinical Target Volume for Intensity Modulated Pelvic Radiotherapy in the Definitive Treatment of Cervix Cancer [33]

For pelvic /Para-aortic radiation, dose should preferably be given as follows (All targets will be treated simultaneously, except as noted.):

- The planning target volume-nodal (PTV nodal) (CTV nodal with 7 -mm margin) will receive 45 Gy. Treatment will be delivered once daily, 5 fractions per week. The planning target volume cervix (PTV cervix) (CTV cervix with 7mm margin) inferiorly and superiorly lateral and posterior margin will be 7-10 mm based upon rectal distension.
- The planning target volume gross node (PTV Node Boost) (GTV node+5mm margin) laterally, posteriorly, inferiorly and superiorly; this volume will not extend into bowel will receive 55 Gy in 25 fractions. Treatment will be delivered once daily, 5 fractions per week.

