4.12 Toxicities and Dosing Delays/Dose Modifications

Any patient who receives treatment on this protocol will be evaluable for toxicity. Each patient will be assessed for the development of toxicity according to the Time and Events table.

Toxicity will be assessed according to the NCI Common Toxicity Criteria for Adverse Events (CTCAE), version 4.0. Dose adjustments should be made according to the system showing the greatest degree of toxicity.

In the absence of treatment delays due to adverse events, treatment may continue for **until completion of all fractions** or until:

- Disease progression
- Inter-current illness that prevents further administration of treatment
- Unacceptable adverse event(s)
- Patient decides to withdraw from the study, **OR**
- General or specific changes in the patient's condition render the patient unacceptable for further treatment in the judgment of the investigator.

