7.2 Safety/tolerability

Analyses will be performed for all patients having received all three fractions of *Image Guided Hypofractionated Radiation Treatment*. The study will use the CTCAE version 4.0 for reporting of non-hematologic adverse events (<http://ctep.cancer.gov/reporting/ctc.html>).

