8. STATISTICAL CONSIDERATIONS

8.1 Primary Endpoint

8.1.1 Study Design/Study Endpoints

The study is a prospective single-arm phase II trial of Image Guided Hypofractionated Radiation Treatment in the definitive treatment of locally advanced cervical cancer. The study will determine whether Image Guided Hypofractionated Radiation Treatment boost is efficacious in women with locally advanced cervical cancer without increased risk of acute GI or GU toxicity. Study endpoints include local control rate, and toxicity assessed by CTCAEv4,

For the safety lead-in not more than 1 of 6 patients should have more than Grade 2 toxicity over 90 days after commencement of Image Guided Hypofractionated Radiation Treatment boost

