8.3 Sample Size

8.3.1 Overview

Six patients will be used for a safety lead-in stage in this phase II clinical trial. In Standard Phase 1 3+3 clinical trials, there is 0 or 1 DLT out of 6 patients at the MTD, which will be used for a subsequent phase II clinical trials. [36] Prior studies have shown the rate of \geq grade 3 GI toxicity to be 7-14% and 2-5% for \geq grade 3 GU toxicity. The treatment will not be considered to be feasible if the rate of acute GI/GU toxicity is $>30\%$. In this phase II clinical trial, six patients will be used in a safety lead-in stage. If there is 0 or 1 DLT out of 6 patients at the safety lead-in stage, we will proceed to a phase II clinical trial. Otherwise, we will stop the trial, and will not proceed to a phase II trial with a given dose.

The primary goal of this study is to assess the 2 year pelvic local control (excluding nodes) from cervix cancer. Historical data shows that the 2 yr-pelvic local control rate is approximately 65%. [4, 5, 9] We expect that this will be increased to 85% with the treatment of cervix Image Guided Hypofractionated Radiation Treatment boost based on best results with Intracavitary/interstitial data [13]. We assume that the loco regional recurrence-free survival follows an exponential distribution. Accrual to the study is assumed to be uniformly distributed over time with no loss to follow-up. Twenty-one patients will achieve 80% power in detecting the difference between the null hypothesis of 2-year recurrence-free survival rate of 65% and the alternative hypothesis of 2-year recurrence-free survival rate of 85% at a two-sided 0.1 significance level assuming a 2-year accrual period and 2-year follow-up period. It is expected that 21 patients will be recruited in 2 years with an expected accrual rate of 10-11 patients per year.

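### The six-patient lead-in has contradictory rules on who counts for toxicity, and either reading can make the go decision too easy

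*Combined protocol and SAP*

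**What the plan says.** The decision rule is in 8.3.1: "If there is 0 or 1 DLT out of 6 patients at the safety lead-in stage, we will proceed to a phase II clinical trial". With two or more, "Otherwise, we will stop the trial, and will not proceed to a phase II trial with a given dose". Section 8.1.1 sets the window: "For the safety lead-in not more than 1 of 6 patients should have more than Grade 2 toxicity over 90 days", counted from commencement of the boost; 2.1 agrees.

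Three places bear on who is counted for toxicity:

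- 4.12: "Any patient who receives treatment on this protocol will be evaluable for toxicity".
- 7.1.1: "All patients will be evaluable for toxicity from the time of their first treatment with radiation". Neither this nor 4.12 sets a minimum boost exposure or length of follow-up.
- 7.2: "Analyses will be performed for all patients having received all three fractions of" the boost. The dose section, 4.1, says "Patients will receive 4 fractions of 7 Gy each via stereotactic body radiation as boost therapy".

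Section 8.5.1 takes the number of patients treated as the denominator of the toxicity proportions. Section 8.4.1 times the acute toxicity analysis for when each patient has at least 90 days of follow-up, there counted from the end of radiation. No section defines a DLT-evaluable patient, replaces a lead-in patient, or classifies one who cannot reach day 90.

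**The concern.** A go rule of at most 1 in 6 has its nominal properties only if all six patients could have shown a DLT and were watched for it. Two features of the plan undermine this, both in the direction of proceeding.

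Under 4.12, 7.1.1 and 8.5.1, an unobserved patient adds to the denominator and cannot add to the numerator. Under 7.2, a patient who stopped the boost because of toxicity may leave the analysis and take her event with her.

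Early exit is plausible here. Eligibility (3.1) admits Zubrod 3, stage up to IVB, poor response to external beam, and co-morbidity that precludes brachytherapy. Section 6.5 allows withdrawal at any time. At stake is the trial's main early protection against a boost whose toxicity exceeds the 30% that 8.3.1 sets as the limit of feasibility.

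**Working it through.** **Inputs.** Go rule, 0 or 1 DLT of 6 (8.3.1). Feasibility limit for acute GI/GU toxicity, 30% (8.3.1). Expected grade 3 or higher rates, GI 7-14% and GU 2-5% (8.3.1), which sum to 9-19% if they do not overlap (my assumption). Early-exit rate: none is given, so it is varied. The plan states no operating characteristic for the lead-in, so there is no figure of its own to reproduce.

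**Six fully observed patients.** With m observed patients and true DLT rate p,

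P(go) = (1 − p)^m + m·p·(1 − p)^(m−1).

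For m = 6, p = 0.30: 0.7^6 + 6(0.3)(0.7^5) = 0.1176 + 0.3025 = 0.420.

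**Reading A (4.12, 7.1.1, 8.5.1): leavers stay in the six as event-free.** If a leaver could show no DLT at all, m falls to 5 or 4 while the rule stays at 0 or 1:

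| True rate | m = 6 | m = 5 | m = 4 |
|---|---|---|---|
| 9% | 0.905 | 0.933 | 0.957 |
| 19% | 0.680 | 0.758 | 0.834 |
| 30% | 0.420 | 0.528 | 0.652 |
| 40% | 0.233 | 0.337 | 0.475 |

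These are upper bounds for one or two leavers, because most leavers would carry some observed risk. If one leaver was observed for a fraction f of her DLT risk, at p = 0.30:

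P(go) = 0.7^5 + 5(0.3)(0.7^4)(1 − 0.3f) = 0.1681 + 0.3602(1 − 0.3f).

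This gives 0.501, 0.474 and 0.447 for f = 0.25, 0.50 and 0.75.

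If each patient independently leaves unobserved with probability d, the visible DLT rate is 0.3(1 − d):

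| Assumed d | Visible rate | P(go) |
|---|---|---|
| 0 | 0.300 | 0.420 |
| 5% | 0.285 | 0.453 |
| 10% | 0.270 | 0.487 |
| 20% | 0.240 | 0.558 |

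**Reading B (7.2): patients short of the stated number of fractions are dropped.** Suppose one of the six stops the boost because of a DLT and the other five each carry a 30% risk.

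- If she counts, the trial proceeds only with no DLT in the other five: 0.7^5 = 0.168.
- If she is dropped and not replaced, it proceeds with 0 or 1 in the other five: 0.528.

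These two figures are conditional on such a patient occurring. The documents give no basis for how often that would be.

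**Later rules in 10.3.** Stopping for more than 3 of the first 9 has probability 0.27 at a 30% rate. Applying the 9- and 15-patient rules after an intact lead-in lowers the chance of passing everything from 0.420 to 0.384, so they do little to repair a weakened lead-in.

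**The case against.** The strongest reply is that no sentence in the plan says an early leaver counts as free of DLT. Section 7.1.1 says when toxicity evaluation begins, not how incomplete follow-up is classified, and 8.4.1 expects 90 days on each patient. This stands as far as it goes: the event-free classification follows from applying 4.12, 7.1.1 and 8.5.1 together and is not stated for the lead-in. But 8.4.1 is silent on a patient who cannot reach 90 days.

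A reader might infer that 4.12 and 7.1.1 are the only evaluability rules and that every treated patient is therefore always among the six. The documents do not support that, because 7.2 sets a third and narrower rule. A woman who stops after one fraction is outside it.

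A reader might also infer that stopping the boost ends observation. It does not. Section 6.3 continues follow-up for five years or until death, and 6.3.1 has toxicity assessed at each visit. Only death, withdrawal of consent or loss to follow-up ends observation. Nor does a patient who never starts the boost clearly enter the count, since her 90-day window never opens.

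Finally, 52.8% and 65.2% assume that one or two of six patients carried no DLT risk at all. That objection is right, and those figures should be read only as ceilings.

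**Conclusion.** The point holds as a contradiction in the lead-in denominator: 4.12, 7.1.1 and 8.5.1 on one side, 7.2 on the other, with 8.3.1 and 8.4.1 silent on incomplete patients. It does not hold as a claim that the plan expressly counts leavers as DLT-free. It matters beyond drafting because both readings err toward proceeding, one by diluting the six and the other by possibly losing an event.

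The size depends on assumed exit. At a true 30% rate, P(go) rises from 42.0% to 45-56% for independent unobserved exit of 5-20%, with ceilings of 52.8% and 65.2% for one and two leavers. With six fully observed patients the concern disappears under Reading A. The figures assume independent patients with a common DLT rate.

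**What to change.** Add to 8.3.1, for the lead-in decision only: a patient counts among the six if she has a DLT within 90 days of boost commencement, whatever number of fractions she received, or if she received all planned boost fractions and was assessed through day 90 without a DLT. Otherwise the next enrolled patient takes her place in the lead-in count, and total enrolment remains 21.

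Reconcile 4.12, 7.1.1, 7.2 and 8.4.1 with this rule, including the three fractions named in 7.2 against the four in 4.1. Keep all treated patients in the safety summaries and the primary analysis.

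With the rule in place, P(go) at a 30% rate among counted patients is the nominal 42.0%. Because every DLT counts but only complete event-free patients do, any remaining tilt is toward stopping. The cost is a paragraph and some cross-references, with no extra patients. The lead-in decision may come later, by the time one more patient needs to reach day 90.
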